#### **5.4 Sample Size and Power**

A typical sensitivity of radiographs for wrist fractures is approximately 65%[5] We estimate that our sensitivity using the Tomo-E system will be approximately 80%. Thus we will need 50 patients to detect this difference, assuming a prevalence of approximately 33% in our test population and with 3 readers, that we will have 70% power to detect differences between the two modalities.

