#### **4.4 Reader Study**

Upon completion of all study image data collection, a reader study will be performed with three MSK fellowship trained radiologists. All images will be reconstructed with our fast-reconstruction algorithm and presented on 3MP viewing monitors with PACS viewing software with conventional zoom/pan/window and level tools. The readers will not be blinded whether the images are from Tomo-E.

Each radiologist will be randomly presented with either the patient's diagnostic radiographs or tomosynthesis study in a random order. They will be asked to review the scan for the presence of a fracture, and comment on location (specific bone) and fracture type. They will be asked their confidence rating on a scale of 0 to 100%.

A washout period of four weeks will be utilized so that the radiologists will have "forgotten" their initial interpretations. At this timepoint, the other modality for each patient will be randomly presented. Diagnostic accuracy will be defined by the presence of a fracture as defined by the clinical diagnosis by the attending orthopedic surgeon at 2 months post imaging during the patients' routine clinical care, such as cast placement, surgery, or follow-up imaging. Sensitivity and specificity to the presence of fractures will be estimated and evaluated between the modalities.

The order that imaging modalities will be presented will be randomly assigned using a computational software in collaboration with the study biostatistician. This randomization schedule will be created prior to the beginning of the reader study and will not be shared with any of the readers.

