For the primary and secondary objective, we will estimate the sensitivity and specificity for a pre-specified cutoff of review scores to detect wrist fracture. Generalized estimating equation will be used to produce such estimates, where diagnosis outcomes from readers are treated as clustered data and a compound symmetry working covariance matrix is used. Normal distributions will be used to construct 95% confidence intervals. Bootstrap method may be used when the normality assumption is of concern. For the AUC analysis, the same estimating procedures will be used to obtain the sensitivity and specificity when varying cutoff scores then the AUC will be calculated using the trapezoidal rule. The confidence of the AUC will be obtained from bootstrap method.

For the confidence study, we expect no missing data or drop out. For any missed data during the reader study, we will question the reader to collect the data. The only primary hypothesis test is whether the mean confidence score is zero with a significance level of 0.05. There is no need to adjust multiple tests. All hypothesis tests that are observed to be not statistically significant will be reported as being inconclusive.

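### The 70% power in section 5.4 does not follow from its stated inputs, and section 5.3 plans no test of the sensitivity difference to which it could belong

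*Combined protocol and SAP*

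**What the plan says.** The primary objective (section 2.1) is to compare the sensitivity of Tomo-E with that of wrist radiography. Section 5.4 takes 65% for radiographs and 80% for Tomo-E, sets N at 50, "assuming a prevalence of approximately 33% in our test population", and concludes "with 3 readers, that we will have 70% power to detect differences between the two modalities". It gives no alpha, sidedness, test, correlation or formula.

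The design is paired. Under section 4.4 each reader sees one modality of a patient first, and after a four-week washout "At this timepoint, the other modality for each patient will be randomly presented". The same section says "Sensitivity and specificity to the presence of fractures will be estimated and evaluated between the modalities".

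Section 5.3 estimates sensitivity by GEE, in which "diagnosis outcomes from readers are treated as clustered data and a compound symmetry working covariance matrix is used", and "Normal distributions will be used to construct 95% confidence intervals". A bootstrap is allowed if normality is in doubt. No correlation value is given and no test of the difference is named. The only alpha belongs elsewhere: "The only primary hypothesis test is whether the mean confidence score is zero with a significance level of 0.05".

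**The concern.** Section 5.4 is the only justification for N = 50 on the primary objective. A reader will take it to mean that the study has a 70% chance of detecting a 15-point gain in sensitivity. Two things stand against that.

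- One third of 50 patients is a small base for sensitivity. The six reads of each patient (three readers, two modalities) are correlated, so they are not six independent observations.
- Power is a property of a specified test. For the sensitivity difference the plan specifies none.

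At stake is whether the funder, the IRB and later readers are given a chance of success that the plan can support.

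**Working it through.** **Inputs from the documents.** Sensitivities 0.65 and 0.80 (difference 0.15), 50 patients, prevalence 0.33, 3 readers, stated power 70% (section 5.4). Paired reading (4.4). Normal-based intervals and clustered reads (5.3).

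**Assumed, because not stated.** Alpha 0.05, one- or two-sided. All correlations, on the binary scale: rb between readers within a modality, rs same reader across modalities, rc different readers across modalities. Readers are treated as fixed.

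**Step 1. Information for sensitivity.** 50 x 0.33 = 16.5 fractured patients. The 95% range of Binomial(50, 0.33) is 10 to 23. Reads per modality: 16.5 x 3 = 49.5.

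**Step 2. Attempt to reproduce 70% by standard calculations.**
- Two independent proportions, pooled variance, 49.5 reads each: 38.5% two-sided, 51.1% one-sided.
- The same with 16.5 per modality: 15.6% and 24.5%.
- All 150 reads per modality, ignoring prevalence: 83.2% and 90.0%.
- McNemar on 49.5 pairs treated as independent: 37% and 50% at zero correlation. It reaches 70% only at a correlation of 0.59 (two-sided) or 0.44 (one-sided).

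The unpaired figures are reference points only; they are not the power of this design.

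**Step 3. Paired and clustered comparison.** The binomial variances are 0.65 x 0.35 = 0.2275 and 0.80 x 0.20 = 0.16, with sum 0.3875. Twice the root of their product is 0.3816. With n fractured patients:

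V = 0.3875 x (1 + 2rb)/3 - 0.3816 x (rs + 2rc)/3; SE = sqrt(V/n); power = Phi(0.15/SE - z), with z = 1.960 two-sided or 1.645 one-sided.

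SE needed for 70%: 0.15/(1.960 + 0.524) = 0.0604 two-sided; 0.15/(1.645 + 0.524) = 0.0691 one-sided. With independent reads the SE is sqrt(0.1292/16.5) = 0.0885.

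Example, (rb, rs, rc) = (.5, .4, .3): V = 0.2583 - 0.1272 = 0.1311; SE = 0.0892; power = Phi(1.682 - 1.960) = 39%.

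Example, all 0.56: V = 0.2738 - 0.2137 = 0.0602; SE = 0.0604; power = Phi(2.484 - 1.960) = 70%.

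| Assumed (rb, rs, rc), n = 16.5 | Two-sided | One-sided |
|---|---|---|
| (0, 0, 0) | 39.6% | 52.0% |
| (.5, .4, .3) | 39.1% | 51.5% |
| (.3, .3, .2) | 42.7% | 55.2% |
| (.5, .5, .4) | 51.5% | 63.8% |
| (.3, .3, .3) | 51.9% | 64.1% |
| (.41, .41, .41) | 58.4% | 70.1% |
| (.5, .5, .5) | 65.0% | 75.8% |
| (.31, .53, .30) | 66.3% | 76.9% |
| (.56, .56, .56) | 70.0% | 79.9% |
| (.5, .6, .5) | 74.0% | 83.1% |

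The largest possible binary correlation between modalities with these sensitivities is sqrt(0.65 x 0.20/(0.80 x 0.35)) = 0.68.

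**Step 4. Chance variation in the number of fractures.** With a common correlation of 0.56, two-sided power is 49% at 10 fractured patients and 83% at 23. The common correlation needed for 70% two-sided is 0.37 at 23, 0.56 at 16.5 and 0.75 at 10. The last exceeds the maximum of 0.68.

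**Step 5. Small-sample behaviour.** Replace the normal by a noncentral t with 16.5 - 1 = 15.5 degrees of freedom and noncentrality 0.15/SE. Two-sided power then falls from 70% to 64% (common 0.56), from 74% to 68% (.5, .6, .5) and from 39% to 35% (.5, .4, .3). A simulation of the normal-approximation test with clustered standard errors (20,000 runs) rejected a true null in 6.4-7.7% of runs at a nominal 5% two-sided. The uncorrected test is therefore somewhat liberal at this size.

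**Step 6. Precision.** Half-width of the 95% CI for a sensitivity of 80% = 1.96 x sqrt(0.16 x (1 + 2rb)/(3n)). For rb from 0.3 to 0.7 this is 14.1-17.3 points at n = 16.5, 18.1-22.2 at n = 10 and 11.9-14.6 at n = 23.

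**The case against.** The strongest reply is that inputs which do not fix a power cannot contradict one. The table itself contains sets that reach 70% or more, and correlations alone are enough at a conventional two-sided 0.05. If the comparison is one-sided, as the wording of the confidence test in 5.3 might suggest, a common correlation of 0.41 suffices. Compound symmetry is the structure that 5.3 names, so the common-correlation rows are arguably closest to the plan. All of this stands, and it rules out calling 70% impossible. But a working covariance structure without a value does not supply the value, and 5.3 gives no sidedness for the sensitivity difference.

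There is also a route without correlations. A one-sided exact test of 50 independent reads against a fixed 65% (39 or more correct) has 71.1% power. It does not rescue the statement: it drops the comparison with radiography and the clustering of reads, whereas 5.4 speaks of detecting differences between two modalities. Nothing in the documents says that it was used.

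Finally, this is labelled a pilot, sensitivity is planned as estimates with intervals, and "All hypothesis tests that are observed to be not statistically significant will be reported as being inconclusive". That limits the harm of a null result. It does not supply the missing assumptions behind a figure that the plan chose to print.

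A reader might infer from the lower rows that the true power is about 40%, or that 50 patients are too few. The documents support neither inference. Every correlation here is assumed, so the table shows how much the answer depends on what is missing and not which answer is likely.

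**Conclusion.** The point holds in this form: the printed inputs do not deliver 70%. Standard two-modality calculations at an assumed alpha of 0.05 give roughly 40-65% two-sided unless correlations are uniformly high or the same reader's two readings are strongly correlated, and a t-based test lowers these values. The figure is unsupported; it is not shown to be unattainable. The gap is more than missing detail, because 70% is the sole basis given for N = 50 and the analysis plan contains no test of the sensitivity difference to which any power could refer. The result rests on assumed alpha, sidedness and correlations and on fixed readers; treating readers as random would lower power further. It should be fixed, but it puts neither enrolment nor the conduct of the study in question.

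**What to change.** **Section 5.3.** Add the between-modality comparison of sensitivity: a GEE with a modality term, clustered by patient, reporting the difference with a 95% CI. Use the bootstrap already allowed there or a small-sample correction. State alpha and sidedness. Reconcile this with the sentence that makes the confidence score the only primary hypothesis test, or say that the sensitivity comparison is estimation only.

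**Section 5.4.** Replace the single 70% with the power, or range of power, for that comparison under stated binary correlations (between readers, same reader across modalities, different readers across modalities). Possible wording: *Of 50 patients, about 16-17 (95% range 10-23) are expected to have a fracture, giving about 50 reads per modality. Power for 80% versus 65% by [test] at [alpha, sidedness], with correlations [values], is [value]; at 10 and 23 fractured patients it is [values].* Do not print the unpaired figure as the design's power.

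Then justify N = 50 as a pilot by precision: a 95% half-width of about 14-17 points for a sensitivity of 80% at 16.5 fractured patients, 18-22 at 10 and 12-15 at 23, for an assumed between-reader correlation of 0.3-0.7.

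**Cost.** A short text and analysis edit in two sections and one recalculation. Enrolment and procedures do not change. The stated power may turn out less favourable.

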#### **5.5 Interim Analysis**

Interim analyses will not be conducted.

### **6. SAFETY MANAGEMENT**

#### **6.1 Unanticipated Adverse Device Effect (UADE)**

The investigational device exemption (IDE) regulations define an unanticipated adverse device effect (UADE) as “any serious adverse effect on health or safety or any life-threatening problem or death caused by, or associated with, a device, if that effect, problem, or death was not previously identified in nature, severity, or degree of incidence in the investigational plan or application (including a supplementary plan or application), or any other unanticipated serious problem associated with a device that relates to the rights, safety, or welfare of subjects” (21 CFR 812.3(s)).

#### **6.2 Unanticipated Problems (UP)**

As defined by UNC’s IRB, unanticipated problems involving risks to study subjects refers to any incident, experience, or outcome that:

- Is unexpected (in terms of nature, severity, or frequency) given (a) the research procedures that are described in the protocol-related documents, such as the IRB-approved research protocol and informed consent document; and (b) the characteristics of the subject population being studied;

- Is related or possibly related to a subject's participation in the research; and
- Suggests that the research places subjects or others at a greater risk of harm (including physical, psychological, economic, or social harm) related to the research than was previously known or recognized.

## 6.3 Reporting

### 6.3.1 UADEs

UADEs must be reported by the clinical investigator to the sponsor and the reviewing IRB, as described below:

For this device study, investigators are required to submit a report of a UADE to the FDA and the UNC IRB as soon as possible, but in no event later than 10 working days after the investigator first learns of the event (§ 812.150(a)(1)), using the MedWatch Form 3500A. Sponsors must immediately conduct an evaluation of a UADE and must report the results of the evaluation to FDA, the UNC IRB, and participating investigators within 10 working days after the sponsor first receives notice of the effect (§§ 812.46(b), 812.150(b)(1)).

For this device study, we will submit a report of a UADE to the IRB as soon as possible, but no later than 10 working days after the investigators first learn of the event.

### 6.3.2 UP

Any events that meet the criteria for "Unanticipated Problems" as defined by UNC's IRB must be reported by the Study Coordinator using the IRB's web-based reporting system.

Any unanticipated problem that occurs during the conduct of this study and that meets at least the first two criteria listed in section 7.2 must be reported to the UNC IRB using the IRB's web-based reporting system.

### 6.3.3 Data and Safety Monitoring Plan

The Principal Investigator will provide continuous monitoring of patient safety in this trial with periodic reporting to an independent Medical Monitor. The medical monitor will review any reported Unanticipated Adverse Device Effects after patients 5, 25, and 50.

Meetings/teleconferences will be held at a frequency dependent on study accrual, and in consultation with the study Biostatistician. These meetings will include the investigators and any other relevant personnel the principal investigators may deem appropriate. At these meetings, the research team will discuss all issues relevant to study progress, including enrollment, safety, regulatory, data collection, etc.

The team will produce summaries or minutes of these meetings. These summaries will be available for inspection when requested by any of the regulatory bodies charged with the safety of human subjects and the integrity of data including, but not limited to, the oversight (Office of Human Research Ethics (OHRE) Biomedical IRB, the Scientific Review Committee (SRC), the Office of Clinical Trials (OCT), or the North Carolina TraCS Institute Data and Safety Monitoring Board (DSMB).

The PI will be responsible for submitting the following information for review by the independent medical monitor: 1) safety and accrual data including the number of study participants imaged; 2) significant developments reported in the literature that may affect the safety of participants or the ethics of the study; 3) preliminary response data; and 4) summaries of team meetings that have occurred since the last report. Findings of the medical monitor review will be disseminated by memo.

## 7. STUDY MANAGEMENT

### 7.1 Institutional Review Board (IRB) Approval and Consent

It is expected that the IRB will have the proper representation and function in accordance with federally mandated regulations. The IRB should approve the consent form and protocol.

In obtaining and documenting informed consent, the investigator should comply with the applicable regulatory requirement(s), and should adhere to Good Clinical Practice (GCP) and to ethical principles that have their origin in the Declaration of Helsinki.

Before recruitment and enrollment onto this study, the patient will be given a full explanation of the study and will be given the opportunity to review the consent form. Each consent form must include all the relevant elements currently required by the FDA Regulations and local or state regulations. Once this essential information has been provided to the patient and the investigator is assured that the patient understands the implications of participating in the study, the patient will be asked to give consent to participate in the study by signing an IRB-approved consent form.

Prior to a patient's participation in the trial, the written informed consent form should be signed and personally dated by the patient and by the person who conducted the informed consent discussion.

### 7.2 Registration Procedures

Study participants will be registered into CRMS, a web based clinical research platform by one of the Study Coordinators.

### 7.3 Data Management and Monitoring/Auditing

The wrist radiograph and Tomo-E scan that are obtained of all eligible enrolled subjects will be de-identified for inclusion in the appropriate readers study. Copies of the clinical report forms as well as the de-identified images described in the preceding will be submitted for each case to the Study Coordinators for maintaining the study record and entering the data into REDCap in preparation for the reader study.

Information regarding why a data value is missing will be documented in the study database in REDCap.

#### 7.4 Adherence to the Protocol

Except for an emergency situation in which proper care for the protection, safety, and well-being of the study patient requires alternative treatment, the study shall be conducted exactly as described in the approved protocol.

#### 7.5 Emergency Modifications

UNC investigators may implement a deviation from, or a change of, the protocol to eliminate an immediate hazard(s) to trial subjects without prior UNC's IRB/IEC approval/favorable opinion.

For any such emergency modification implemented, an IRB modification form must be completed by UNC Research Personnel within five (5) business days of making the change.

#### 7.6 Protocol Deviations/Violations

According to UNC's IRB, a protocol deviation is any unplanned variance from an IRB approved protocol that:

- Is generally noted or recognized after it occurs
- Has no substantive effect on the risks to research participants
- Has no substantive effect on the scientific integrity of the research plan or the value of the data collected
- Did not result from willful or knowing misconduct on the part of the investigator(s).

An unplanned protocol variance is considered a violation if the variance meets any of the following criteria:

- Has harmed or increased the risk of harm to one or more research participants.
- Has damaged the scientific integrity of the data collected for the study.
- Results from willful or knowing misconduct on the part of the investigator(s).
- Demonstrates serious or continuing noncompliance with federal regulations, State laws, or University policies.

If a deviation or violation occurs please follow the guidelines below:

**Protocol Deviations:** UNC personnel will record the deviation and report to any sponsor or data and safety monitoring committee in accordance with their policies. Deviations should be summarized and reported to the IRB according to the UNC IRB reporting requirements.

**Protocol Violations:** Violations should be reported by UNC personnel within one (1) week of the investigator becoming aware of the event using the same IRB online mechanism used to report Unanticipated Problems.

#### Unanticipated Problems:

Any events that meet the criteria for "Unanticipated Problems" as defined by UNC's IRB must be reported by the study team using the IRB's web-based reporting system.

## **7.7 Amendments to the Protocol**

Should amendments to the protocol be required, the amendments will be originated and documented by the Principal Investigator at UNC. It should also be noted that when an amendment to the protocol substantially alters the study design or the potential risk to the patient, a revised consent form might be required.

The written amendment, and if required the amended consent form, must be sent to UNC's IRB for approval prior to implementation.

## **7.8 Record Retention**

Study documentation includes all eCRFs, data correction forms or queries, source documents, Sponsor-Investigator correspondence, monitoring logs/letters, and regulatory documents (e.g., protocol and amendments, IRB correspondence and approval, signed patient consent forms).

Source documents include all recordings of observations or notations of clinical activities and all reports and records necessary for the evaluation and reconstruction of the clinical research study.

Government agency regulations and directives require that all study documentation pertaining to the conduct of a clinical trial must be retained by the study investigator. In the case of a study with a drug seeking regulatory approval and marketing, these documents shall be retained for at least two years after the last approval of marketing application in an International Conference on Harmonization (ICH) region. In all other cases, study documents should be kept on file until three years after the completion and final study report of this investigational study.

## **7.9 Obligations of Investigators**

The Principal Investigator is responsible for the conduct of the clinical trial at the site in accordance with Title 21 of the Code of Federal Regulations and/or the Declaration of Helsinki. The Principal Investigator is responsible for personally overseeing the treatment of all study participants. The Principal Investigator must assure that all study site personnel, including sub-investigators and other study staff members, adhere to the study protocol and all FDA/GCP/NCI regulations and guidelines regarding clinical trials both during and after study completion.

## **7.10 Conflict of Interest**

Any investigator who has a conflict of interest (COI) with this study as defined by the policies of the University of North Carolina will have the conflict reviewed by a properly constituted Conflict of Interest Review Committee with a committee-sanctioned conflict management plan that has been reviewed and approved by the IRB prior to participation in this study. All University of North Carolina investigators will follow the University conflict of interest policy.

